4.4.1 Adverse Events

A summary table of adverse events will include the following information:

- number of patients exposed to study treatment,
- number of patients experiencing at least one AE,
- number of patients experiencing at least one severe AE,

- number of patients experiencing at least one serious AE,
- number of patients experiencing at least one drug-related AE,
- number of deaths,
- total number of patients withdrawn,
- number of withdrawals due to AEs.

All adverse experiences will be coded using MedDRA (Medical Dictionary for Regulatory Activities) and will be summarized by MedDRA System Organ Class (SOC) and Preferred Term. Adverse events will be defined as: 1) AEs that occurred or worsened (increased in intensity and/or frequency) on or after the first dose of study medication, 2) AEs with a missing start date or a stop date on or after the first dose of study medication, 3) AEs with both a missing start and stop date. Events that occur within 14 days after treatment discontinuation will also be considered AEs. Serious adverse events that occur within 30 days after treatment discontinuation will be included in the database.

Adverse events will be summarized using the total number of AEs, the total number and percent of patients who experience an AE, and the number and percent of patients who experienced an AE within each SOC (and preferred term within an SOC). The rate of each AE (per 100 patient years) will also be calculated. AEs will also be presented by intensity (mild, moderate, severe), by seriousness (serious, non-serious), and by relationship to study medication (at least possibly related, not related). The number and percentage of patients who are withdrawn from the study due to AEs will be calculated, and the AEs involved will be summarized in a frequency table. Time to onset and duration of all AEs with an incidence of >5%, and of any AEs of special interest (e.g., worsening of dystonia), will be summarized with descriptive statistics.

Patients who have experienced the same AE multiple times will be counted only once for the corresponding preferred term. Similarly, if a patient experiences multiple AEs within the same SOC, that patient will be counted only once for that SOC. AEs will be tabulated by presenting SOCs alphabetically and, within each SOC, presenting the preferred terms in decreasing order of the total number of patients who experienced each type of AE. In summaries presenting the incidence of AEs by intensity, seriousness, and relation to study medication, a patient with multiple events coded to a given preferred term or SOC will be counted only once for that preferred term or SOC according to the most severe event, the most serious event, or the event with the closest relationship to study medication.

Listings of SAEs, of withdrawals due to AEs, and of deaths will be provided separately and described in patient narratives.

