7.2 Safety Measurements

7.2.1 Adverse Events and Serious Adverse Events

7.2.1.1 Definition of Adverse Events

An adverse event (AE) is any untoward medical occurrence in a patient who is administered a pharmaceutical or other therapeutic product in a clinical study, not necessarily having a causal relationship with the product. An AE can therefore be any unfavorable and unintended sign, symptom, or disease temporally associated with the use of a product, whether or not considered related to that product.

AEs include:

- Exacerbation of a pre-existing illness, including acute episodes/crisis of a chronic underlying condition
- An increase in frequency or intensity of a pre-existing episodic event or condition
- A condition detected or diagnosed after study treatment administration, even though it may have been present prior to the start of the study
- A continuous persistent disease or symptom present at baseline that worsens following the start of the study
- Accidents (e.g., involving a motor vehicle)
- Reasons for changes in concomitant medication (type of drug and/or dose)
- Medical, nursing, or pharmacy consultation
- Admission to hospital and surgical operations
- Abnormalities in laboratory findings (e.g., blood chemistry, hematology, urinalysis), ECG, or other assessments (e.g., vital signs) that are not part of a larger medical condition already recorded as an AE and which are judged by the investigator to be clinically significant. The investigator should exercise medical and scientific judgment in deciding whether an abnormal laboratory finding or other abnormal assessment is clinically significant.

AEs do not include:

- A pre-existing disease or condition present or detected at the start of the study that does not worsen
- Hospital admissions or surgical procedures that had been planned prior to enrolment into the study

- The disease or disorder being studied, or a sign or symptom associated with that disease or disorder, unless it has worsened
- An overdose of either the study treatment or concurrent medication without any signs or symptoms

Note: A case of overdose that is not associated with an AE is to be documented as a protocol deviation and promptly reported to the Medical Monitor.

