9.4.1.4 Analysis of Safety

All safety data reported and collected during deferiprone therapy for all patients will be presented in listings and summary tables to give an overview of the safety findings. For patients continuing on deferiprone in the extension study, this time period will be from the start of TIRCON2012V1 to the completion of TIRCON2012V1-EXT; for those who received placebo in the initial study and are switching to deferiprone in the extension study, it will be from the start to the completion of the extension study.

Adverse Events:

A summary table of adverse events will include the following information:

- Number of patients exposed to study treatment
- Number of patients experiencing at least one AE
- Number of patients experiencing at least one severe AE
- Number of patients experiencing at least one serious AE
- Number of patients experiencing at least one drug-related AE
- Number of deaths
- Total number of patients withdrawn
- Number of withdrawals due to AEs

All adverse experiences will be coded using MedDRA (Medical Dictionary for Regulatory Activities) and will be summarized by MedDRA System Organ Class (SOC) and Preferred Term. Adverse events will be defined as: 1) AEs that occurred or worsened (increased in intensity and/or frequency) on or after the first dose of study medication, 2) AEs with a

missing start date and a stop date on or after the first dose of study medication, 3) AEs with both a missing start and stop date. Events that occur within 14 days after treatment discontinuation will also be considered AEs. Serious adverse events that occur within 30 days after treatment discontinuation will be included in the database.

Adverse events will be summarized using the total number of AEs, the total number and percent of patients who experience an AE, and the number and percent of patients who experienced an AE within each SOC (and preferred term within an SOC). AEs will also be presented by intensity (mild, moderate, severe), by seriousness (serious, non-serious), and by relationship to study medication (at least possibly related, not related). The number and percentage of patients who are withdrawn from the study due to AEs will be calculated, and the AEs involved will be summarized in a frequency table. Time to onset and duration of all AEs with an incidence of >5%, and of any AEs of special interest (e.g., worsening of dystonia), will be summarized with descriptive statistics.

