3.5 Missing Data Handling and Derivation Rules

For safety data analysis, no imputation will be performed on the missing data and analysis will be based on observed cases.

For efficacy endpoints, the continuous variables will be summarized and analyzed as recorded on the case report forms (CRFs). If statistically significant imbalances are detected in the incidence of changes in DBS settings and outcome impacting medication use as well as the frequency of PRN drug or rescue medication between the initial study and the extension study, a Mixed-Effect Model Repeated Measure (MMRM) model will be used as the analysis method to compare the change in score from baseline between the initial study and the extension study for patients who received placebo in initial study (TIRCON2012V1) and the analysis will be based on observed cases. If no significant imbalance was detected, the paired t-test will be used as the analysis method and the last observed data will be used.

For the efficacy analysis on all patients who received DFP during the initial and the extension study, the last observation will be used to calculate the change from baseline for patients terminated early. As a sensitivity analysis, for early termination due to worsening of disease conditions or inadequate efficacy of the drug, as indicated in the CRF, the “worst score” method will be used for data imputation. That is, for continuous variables such as BAD total score at a particular time point, the worst score of all patients will be used to impute the missing data at that time point. For categorical variable such as responder, the worst category (treatment failure) will be assigned. For missing data due to missed visit, the last observation will be used to fill the void.

For BAD total score, if one or several component scores cannot be measured, then the same component score from the last visit will be carried forward and if it is also missing, the score from the next visit will be carried backward to fill the missing component score(s) before the total score is calculated.

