Date of exposure will be defined as day 1 for all duration calculations. For example, age at entry will be calculated as the integer value of the expression: (date of exposure – date of birth) / 365.25. For patients on DFP in the initial study, the date of exposure during the initial study (TIRCON2012V1) will be used while for those switched from placebo to DFP in the extension study (TIRCON2012V1-EXT), the date of exposure during the extension study will be used.

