4.4 Safety Analyses

The safety endpoints include:

- Adverse events (AEs): Frequency, severity, time to onset, duration, and relatedness to study product
- Serious adverse events (SAEs): Frequency, severity, time to onset, duration, and relatedness to study product

-
- Number of discontinuations due to AEs
 - Hematology assessments
 - Blood chemistry assessments
 - ECG assessments

All safety data collected will be presented in listings and summary tables or graphs to give an overview of the safety findings. All safety endpoints will be analyzed based on the safety population. For patients continuing on deferiprone in the extension study, this time period will be from the start of TIRCON2012V1 to the completion of TIRCON2012V1-EXT; for those who received placebo in the initial study and are switching to deferiprone in the extension study, it will be from the start to the completion of the extension study.

For those patients who do not follow the scheduled time window exactly for each visit or withdraw from the study early, the following time window will be employed to classify the safety data into each scheduled visit according to the time elapsed from the first medication date (date of exposure) to the assessment date:

Month 1.5 visit: 0.75 to <2.25 months

Month 3 visit: 2.25 to <4.5 months

Month 6 visit: 4.5 to <9 months

Month 12 visit: 9 to <15 months

Month 18 visit: 15 to <21 months

Month 24 visit: 21 to <27 months

Month 30 visit: 27 to <33 months

Month 36 visit: 33 to <39 months

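### SAP 4.4.1 defines countable adverse events with *or* where the protocol has *and*, so read literally it counts two date patterns that the protocol leaves out

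*SAP*

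**What the plan says.** Protocol 9.4.1.4 and SAP 4.4.1 each define countable adverse events by three rules. Rule 1 (onset or worsening on or after first dose) and rule 3 ("AEs with both a missing start and stop date") are the same in both, as are the sentences on the 14-day and 30-day windows after treatment stops. Rule 2 differs by one word:

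- Protocol 9.4.1.4 requires a "missing start date and a stop date on or after the first dose of study medication".
- SAP 4.4.1 admits "AEs with a missing start date or a stop date on or after the first dose of study medication".

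Four other provisions bear on the point:

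- Protocol 7.2.1.1 lists among things that are not adverse events: "A pre-existing disease or condition present or detected at the start of the study that does not worsen".
- SAP 3.5 says of missing safety data: "For safety data analysis, no imputation will be performed on the missing data and analysis will be based on observed cases".
- SAP 4.4 sets the safety period for patients who switched from placebo: "it will be from the start to the completion of the extension study".
- SAP 3.5 fixes the time origin: "Date of exposure will be defined as day 1 for all duration calculations", and "for those switched from placebo to DFP in the extension study (TIRCON2012V1-EXT), the date of exposure during the extension study will be used".

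**The concern.** Under the protocol's rule 2 an event with no start date is counted only if its stop date shows that it was still present at or after first dose. Under the SAP's wording either condition is enough. An event with a known start before treatment then qualifies merely because it resolved on treatment, and an event with no start date qualifies even if it ended before treatment.

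Adverse event frequency is part of the first primary endpoint (Protocol 9.1.1). This rule decides which events enter the patient counts and the rates per 100 patient-years in SAP Table 14.3.1.2 and the related tables. Those tables pool all patients in a single deferiprone column. An event that began on placebo and resolved after the switch would therefore appear as a deferiprone event, with nothing in the table to show it.

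Such an event would also have its onset before day 1. SAP 4.4.1 plans onset and duration summaries for all adverse events above 5% incidence. The only shell that displays them, Table 14.3.1.8, covers adverse drug reactions, so as the shells stand the onset problem shows only for events classed as reactions.

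**Working it through.** **Inputs.** Rules 1 to 3 from Protocol 9.4.1.4 and SAP 4.4.1; 68 patients enrolled, 44 formerly on deferiprone and 24 formerly on placebo (SAP 3.2); planned deferiprone exposure of 3 years or 1.5 years respectively (Protocol 1.2). The plan gives no figure of its own to reproduce here.

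**Step 1: date patterns.** Start and stop can each be before first dose, on or after it, or missing, which gives 3 × 3 = 9 combinations. A start on or after first dose with a stop before it is impossible, leaving 8. For an event that does not worsen on treatment:

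| Start | Stop | Protocol (*and*) | SAP (*or*, literal) |
|---|---|---|---|
| before | before | no | no |
| before | on/after | no | **yes (a)** |
| before | missing | no | no |
| on/after | on/after | yes, rule 1 | yes |
| on/after | missing | yes, rule 1 | yes |
| missing | before | no | **yes (b)** |
| missing | on/after | yes, rule 2 | yes |
| missing | missing | yes, rule 3 | yes |
| **Counted** | | **4 of 8** | **6 of 8** |

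No pattern that the protocol counts is lost. For events that did worsen on treatment, rule 1 already applies and the two texts agree on every pattern.

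**Step 2: is *or* intended?** Three features suggest not.

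- Under *or*, any missing start date already qualifies, so rule 3 captures nothing further. Under *and*, rule 3 is needed for the pattern with both dates missing.
- The literal rule counts a non-worsening event from before treatment if it resolves on treatment, but not if it carries on with no stop date.
- It also counts an event that ended before any dose, provided its start date is missing.

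**Step 3: conflict with other text.** Pattern (a) runs against Protocol 7.2.1.1, which excludes pre-existing conditions that do not worsen. Pattern (b), for a placebo switcher, can lie outside the safety period in SAP 4.4. Because SAP 3.5 rules out imputing safety data, a missing start date stays missing, and rule 2 decides whether a pattern (b) event is counted under the definition.

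**Step 4: other readings of the SAP sentence.**

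- If it means that one date is missing and the other is on or after first dose, the count is 4, the same set as the protocol.
- If it means that either date is missing, without further condition, the count is 6, but with a different added pair: missing start with stop before first dose, and start before first dose with stop missing.

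**Step 5: size per event.** Assuming that all 68 patients complete planned exposure:

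- Exposure = 44 × 3 + 24 × 1.5 = 132 + 36 = 168 patient-years.
- One extra event = 100 / 168 = 0.60 per 100 patient-years.
- Exposure 10% lower: 100 / (0.9 × 168) = 0.66.
- Exposure 20% lower: 100 / (0.8 × 168) = 0.74.
- One patient counted only because of such an event = 1 / 68 = 1.5 percentage points.

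**The case against.** The strongest reply is that other text already blocks most of the extra capture. The safety period in SAP 4.4 should remove a switcher's event that ended before the first deferiprone dose. For the 44 continuing patients, pattern (b) needs an event that ended before any study drug. Rule 2 also selects among events already recorded as adverse events, and Protocol 7.2.1.1 keeps non-worsening pre-existing conditions out of those records, so pattern (a) should be nearly empty in that group. What realistically remains is an event that began on placebo in one of the 24 switchers and resolved after the switch, and the documents do not say whether such records reach the analysis dataset. One reading of the sentence gives no difference at all. Four against six counts logical cells, not events. Safety reporting is descriptive and single-arm.

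Much of this stands as a limit on reach. The no-imputation rule matters only for pattern (b), and no expected number of events can be given. It does not remove the fault. Protocol 7.2.1.1 contradicts the literal rule; it does not correct it. The remaining case is plausible, because the last visit of the initial study is Visit 1 of the extension and adverse events are followed until they resolve or stabilise (Protocol 5.1 and 7.2.1.2). If its record is in the dataset, the literal rule counts it. A rule open to three readings with different results also needs correcting for that reason alone.

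**Conclusion.** The concern holds. SAP 4.4.1 rule 2 departs from Protocol 9.4.1.4 by one word, probably by accident, and followed literally it counts 6 of 8 date patterns for non-worsening events where the protocol counts 4. The wording difference is certain; the number of events affected is unknown. For the 24 switchers it depends on whether adverse event records from the placebo period enter the analysis dataset. Each wrongly counted event adds 0.60 per 100 patient-years on full planned exposure, or 0.66 to 0.74 if exposure is 10% to 20% lower. The error can only inflate adverse event counts; it cannot hide harm, and efficacy is untouched. It should still be corrected, because this is an operative rule for the primary safety endpoint.

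**What to change.** In SAP 4.4.1 rule 2, replace *or* with *and*, so that the rule again requires a "missing start date and a stop date on or after the first dose of study medication". The SAP then counts the same 4 patterns as the protocol, and rule 3 regains its purpose. As a clarification only, add that first dose of study medication means the date of exposure to deferiprone as defined in SAP 3.5. The cost is one word and an optional cross-reference, with no new data and no new table.

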4.4.2 Laboratory Data

Descriptive statistics for each clinical laboratory test will be presented for each visit as defined above for hematology and for blood biochemistry. For each test, if multiple measurements are taken on the same scheduled visit for a subject, average value will be used for this subject at that visit. According to the laboratory normal ranges, laboratory test results will be categorized as low (< lower normal limit), normal (within normal range), and high (> upper normal limit). Shift tables comparing the distributions of these three categories at baseline versus end of study for parameters of interest will be presented.

Continuous data will also be presented graphically for examination of possible trends.

Clinically significant laboratory values will be reported in the adverse event analysis.

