7.2.2 Laboratory Measurements

Samples for laboratory safety assessments will be taken at the time points indicated below. If a patient withdraws from the study, the End of Study procedures are to be performed at an early termination visit.

Hematology: Complete blood count (CBC), including total WBC, ANC, platelet count, and hemoglobin	Weekly
Blood chemistry: Serum ferritin, total protein, GGT, LDH, sodium, potassium, chloride, glucose, total, bilirubin, AST, ALT, albumin, blood urea nitrogen, calcium, creatinine, uric acid, alkaline phosphatase, and amylase	Visits 1, 2, 3, and 4
Urinalysis: pH, specific gravity, glucose, protein, ketones, and blood. If indicated by the dipstick, sediment microscopy will be performed.	Visits 1, 2, 3, and 4
Pregnancy testing: Serum pregnancy tests will be performed for all sexually active females of childbearing potential (unless the investigator determines there is no reasonable risk of pregnancy because of significant incapacity)	Visits 1, 2, 3, and 4

The investigator must review and interpret each laboratory report, and document the review by signing or initialing and dating the report. Any laboratory values that fall outside a clinically accepted range, or values that differ significantly from previous values, must be marked by the investigator as either “CS” (clinically significant) or “NCS” (not clinically significant). Any that are marked as CS must be further explained and documented as an AE.

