Patients who have experienced the same AE multiple times will be counted only once for the corresponding preferred term. Similarly, if a patient experiences multiple AEs within the same SOC, that patient will be counted only once for that SOC. AEs will be tabulated by presenting SOCs alphabetically and, within each SOC, presenting the preferred terms in decreasing order of the total number of patients who experienced each type of AE. In summaries presenting the incidence of AEs by intensity, seriousness, and relation to study medication, a patient with multiple events coded to a given preferred term or SOC will be counted only once for that preferred term or SOC according to the most severe event, the most serious event, or the event with the closest relationship to study medication.

Listings of SAEs, of withdrawals due to AEs, and of deaths will be provided separately and described in patient narratives.

ECG:

Clinically significant ECG abnormalities will be reported. The number and percentage of patients with normal and abnormal ECG results will be provided.

Vital Signs

Descriptive statistics (mean, median, standard deviation, minimum and maximum) will be presented for temperature, heart rate, respiratory rate, systolic blood pressure, diastolic blood pressure, weight, and height, at baseline and each relevant visit. Data will also be presented graphically for examination of possible trends.

Biochemistry and Hematology:

Descriptive statistics for each clinical laboratory test will be presented for each scheduled visit. According to the laboratory normal ranges, laboratory test results will be categorized as low (< lower normal limit), normal (within normal range), and high (> upper normal limit). Shift tables comparing the distributions of these 3 categories at baseline versus end of study will be presented. Continuous data will also be presented graphically for examination of possible trends.

Clinically significant laboratory values will be reported in the AE analysis.

Concomitant Medications

Medications will be coded using the WHO Drug dictionary. Medications taken during the course of the trial (on or after the first study drug dose and before or on the study termination date) will be considered as concomitant medications. Medications started after the study termination date will not be reported in tables, but will be presented in patient data listings. Concomitant medications used to treat adverse events will be differentiated from others.

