14.3.2 Hematology and Biochemistry and Urinalysis	
Table 14.3.2.1.1	Hematology at each follow-up visit – safety population
Table 14.3.2.1.2	Hematology analysis: change in value at the end of study (Visit 4) – safety population
Table 14.3.2.1.3	Shift table comparing three laboratory value categories at baseline and end of study: Hematology – safety population
Table 14.3.2.2.1	Blood biochemistry at each follow-up visit – safety population
Table 14.3.2.2.2	Blood biochemistry analysis: change in value at the end of study (Visit 4) – safety population
Table 14.3.2.2.3	Shift table comparing three laboratory value categories at baseline and end of study: Blood biochemistry – safety population

Table 14.3.2.3.1 Proportions of abnormal urinalysis results in each visit – safety population

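### The planned hematology tables give no per-patient lowest ANC, do not use the protocol's neutropenia cut-offs, and omit the out-of-range incidence stated in the synopsis

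*SAP*

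**What the plan says.** Protocol 9.1.1 lists hematology assessments among the primary endpoints. Protocol 7.2.1.8 names neutropenia as an important event with a known association with deferiprone. It grades a confirmed ANC as mild (1.0 to <1.5), moderate (0.5 to <1.0) or severe (<0.5, all x10^9/L). Counts are weekly (Table 5.1) and daily during an episode until it resolves.

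Protocol 9.4.1.4 asks for visit summaries: "Descriptive statistics for each clinical laboratory test will be presented for each scheduled visit". It also asks for baseline-to-end shift tables. The synopsis, under statistical methods, adds that the incidence of out-of-range laboratory values will be tabulated, and lists this separately from the shift tables.

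SAP 4.4.2 presents hematology by visit, referring back to a definition given earlier, and adds: "if multiple measurements are taken on the same scheduled visit for a subject, average value will be used for this subject at that visit". The earlier definition is in SAP 4.4: "the following time window will be employed to classify the safety data into each scheduled visit according to the time elapsed". One such window is "Month 12 visit: 9 to <15 months". The sentence that introduces the windows limits them to patients who are off schedule or withdraw early.

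For categories, SAP 4.4.2 classifies results by laboratory normal range and states: "Shift tables comparing the distributions of these three categories at baseline versus end of study for parameters of interest will be presented". The hematology tables in the SAP's list are 14.3.2.1.1 (statistics per visit, including a minimum and maximum), 14.3.2.1.2 ("Hematology analysis: change in value at the end of study (Visit 4) – safety population") and 14.3.2.1.3 (the shift table).

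**The concern.** Neutropenia can come and go between two six-monthly visits. A useful laboratory summary of that risk says how low each patient's count fell and how many patients crossed each cut-off. None of the three planned tables does this. The shift table looks only at the two ends of follow-up and uses the laboratory's range, not 1.5, 1.0 and 0.5. The visit table's minimum is the lowest visit value across patients, after any averaging.

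The averaging rule adds a second difficulty. It is unclear whether a visit value is one count or the mean of everything in a window. Two programmers following the text could produce different tables, and one of those tables would dilute low counts heavily.

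At stake is whether the laboratory part of a primary endpoint can be set beside the adverse-event counts.

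**Working it through.** **1. Tables against commitments.**

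| Item | Hematology table in the SAP? |
|---|---|
| Statistics per visit (Protocol 9.4.1.4) | Yes, 14.3.2.1.1 |
| Baseline-to-end shift (Protocol 9.4.1.4) | Yes, 14.3.2.1.3 |
| Out-of-range incidence (synopsis) | None of its own; the shift shell's totals give category counts at baseline and end of study only |
| Lowest ANC per patient | None |
| ANC by the cut-offs of Protocol 7.2.1.8 | None |

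This part needs no assumption.

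**2. Which counts make up a visit?** The reference back in 4.4.2 points to the windows in 4.4 and so to pooling. Three things point the other way: the lead-in limiting the windows to off-schedule or early-withdrawn patients, the averaging rule's restriction to the same scheduled visit, and Table 5.1, which puts weekly draws in a separate column. Week 3 falls at (7×3+1)/30.4375 = 0.72 months, before the first window opens at 0.75, so draws in weeks 1 to 3 belong to no window. The text leans towards visit-day counts but does not settle it.

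**3. If counts are pooled into windows.** Placing week k at (7k+1)/30.4375 months gives 6, 10, 19 and 27 weekly draws in the Month 1.5, 3, 6 and 12 windows. Month 18 has 13 for placebo switchers and 26 for patients continuing deferiprone.

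The documents give no ANC levels or episode lengths. Assumptions (x10^9/L): usual ANC 2.5 to 4.0; low counts 1.0 to 1.4 (mild), 0.5 to 0.9 (moderate), 0.1 to 0.45 (severe); daily counts for 3, 7 or 14 days, then two recovery counts of 1.5; onset equally likely in each week. Mild cases stay in the study. Moderate and severe cases are withdrawn (Protocol 4.5), which cuts the window short.

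- Mild, 7 days at 1.2, usual 3.0, in a window of 26 weekly slots (two replaced by episode counts): (24×3.0 + 7×1.2 + 2×1.5)/33 = 83.4/33 = 2.53. Not low.
- Severe, at 0.3, usual 3.0, with k earlier counts in the window: mean = (3.0k + 0.3L + 3.0)/(k + L + 2). For L=7, k=5: 20.1/14 = 1.44. For L=14, k=11: 40.2/27 = 1.49. For L=14, k=0: 7.2/16 = 0.45. For L=14, k=1: 10.2/17 = 0.60.

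Share of onset weeks in which some window mean falls below the stated cut-off (range over the assumed levels):

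| | 3 days | 7 days | 14 days |
|---|---|---|---|
| Mild, <1.5 (switchers) | 0% | 0% | 0–8% |
| Moderate, <1.0 (switchers) | 0–6% | 0–17% | 10–36% |
| Severe, <0.5 (switchers) | 0% | 0–9% | 0–22% |
| Severe, <1.5 (switchers) | 15–35% | 24–62% | 47–92% |
| Severe, <0.5 (continuing, weeks 79–156) | 0% | 0–4% | 0–12% |

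A long severe episode often pulls a window mean below 1.5, but seldom below 0.5.

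**4. If only visit-day counts are used.**

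- *Mild, patient stays in.* Switchers have 3 post-baseline visits in 78 weeks (546 days). Continuing patients have 8 in 156 weeks (1092 days): five in the initial study (Protocol 1.2) and three in the extension. The chance of overlapping a visit is 3L/546 = 3.8% (7 days) or 7.7% (14 days), and 8L/1092 = 5.1% or 10.3%.
- *Moderate or severe, patient withdrawn.* Early Termination includes hematology and is due as soon as possible, within 30 days of the last dose (Protocol 5.1). If it is uniform over days 0 to D, the count is still low with probability L/(D+1), capped at 1:

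| Visit within | 3 days | 7 days | 14 days |
|---|---|---|---|
| 0–30 days | 10% | 23% | 45% |
| 0–14 days | 20% | 47% | 93% |
| 0–7 days | 38% | 88% | 100% |

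The result therefore turns on how prompt the visit is. Even then the shift table would say only *low*, without the protocol category.

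**The case against.** The strongest reply is that neutropenia does not depend on these tables. Every grade goes on the SAE form (Protocol 7.2.1.8). For laboratory values in general, "Any that are marked as CS must be further explained and documented as an AE", and SAP 4.4.2 repeats that "Clinically significant laboratory values will be reported in the adverse event analysis". AE tables with rates per 100 patient-years, withdrawals, narratives, the hematology listing and per-patient ANC plots follow. All of this stands. A reader might infer that a neutropenia signal would be hidden or lost; the documents do not support that. What remains is narrower. AE intensity is graded by discomfort or impairment, with CTCAE only recommended (Protocol 7.2.1.4), so the AE tables need not reproduce the ANC categories. Low counts judged not clinically significant reach only the listings and plots.

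A reader might also infer that the SAP shows no low ANC at all, or that six-month averaging is planned. Neither follows. Table 14.3.2.1.1 prints a minimum at each visit, and the wording leans towards visit-day counts. Nor can one say in general that moderate or severe episodes would usually be missed: with visit-day counts and a prompt Early Termination visit, many would show as the minimum or as *low* at the end of study.

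Finally, the SAP does deliver what Protocol 9.4.1.4 asks for, and a lowest-ANC table is good practice rather than a commitment. That is fair. The out-of-range incidence is stated in the synopsis, though, and the shift totals meet it only at two time points.

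**Conclusion.** The point holds as a minor gap in laboratory summary. From the text alone: no table of each patient's lowest ANC, none using the protocol's cut-offs, no separate out-of-range incidence table for hematology, and no clear rule on which counts enter a visit value.

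The effect depends on that rule. With pooling, a brief neutropenia would usually not appear at its protocol category: at most 36% of onset weeks in any case examined, and 0% in many. With visit-day counts, a mild episode that resolves between visits would usually not appear (overlap of 3.8% to 10.3% for 7 to 14 days). For a moderate or severe episode the chance runs from 10% to 100%, according to its length and the timing of Early Termination.

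These percentages rest on assumed ANC levels, episode lengths and uniform onset. They show direction and rough size only. The missing tables do not depend on them.

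**What to change.** In SAP 4.4.2 and the table list:

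- Add a table of each patient's lowest ANC after the first deferiprone dose, by the protocol cut-offs (<1.5, <1.0, <0.5 x10^9/L), confirmed and unconfirmed. Use all weekly counts (including weeks 1 to 3), repeat counts (including those taken after deferiprone is stopped) and Early Termination counts.
- Add a baseline-to-worst shift for ANC, WBC, platelets and hemoglobin beside the baseline-to-end shift.
- Add the out-of-range incidence table stated in the synopsis.
- State which counts enter the visit summaries. The count closest to the nominal visit day would be one clear choice. This removes the ambiguity but does not by itself show low points, so it does not replace the tables.

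The lowest-ANC table puts every confirmed episode in its category, however a visit is defined. The cost is a few lines of SAP text and about three tables from data already collected; SAP section 5 already allows tables to be added. The one consequence to expect is that more patients will be shown as out of range than in the baseline-to-end tables.
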